1.9 Study Rationale

By employing a combination of advanced MRI techniques and correlative serum biomarkers of BBB disruption, we plan to develop a powerful, first of its kind clinical algorithm in pediatrics whereby we can measure and identify the window of maximal BBB disruption post MLA to 1) allow for an alternative to surgery in incompletely resected tumors, 2) allow for optimal chemotherapeutic dosing to achieve the greatest benefits and the least systemic side effects and 3) distinguish subsequent tumor progression from long-term MLA treatment effects. Preliminary data in adult imaging studies have shown that the BBB disruption lasts for several weeks following treatment before returning to a low baseline. This pilot therapeutic study will provide preliminary validation in pediatric patients.

Although we have a large armamentarium of cytotoxic drugs with potential activity against brain tumors, the vast majority has poor CNS penetration limiting their usefulness. Our proposed use of MLA to achieve both cytoreduction and increased permeability of the peritumoral BBB has the potential to be practice changing and will allow us to test many drugs that have not shown promise due to poor BBB penetration. The innovative algorithm

to detect and measure MLA-induced peritumoral BBB compromise may also be applied using other treatments.

Recent work has collectively demonstrated striking immune dysregulation in patients with GBM, including T cell lymphopenia and anergy, cytokine dysregulation, and increased regulatory T cell (T_{reg}) populations among others, which reflect immunologic compromise and functional impairment[54-57]. However, a growing list of potential tumor antigens has been identified, suggesting that tumor-specific recognition by immune cells may be biologically relevant and therapeutically exploitable[55, 58]. Therefore, given the immune dysfunction characterized in GBM patients, approaches that potentiate the anti-glioma immune response are particularly exciting. A priori, because the immune system has evolved to recognize a tremendous diversity of antigenic epitopes in vertebrates, immune-potentiating efforts – with MLA being one potential approach – may be especially effective at targeting the heterogeneity that defines GBM.

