5.5 Evaluability Criteria

All patients are evaluable for toxicity. Patients are evaluated from first receiving study treatment until a 30-day follow up after the conclusion of treatment or death. Patients on Arm A will be followed for a minimum of 6 months or death.

All patients in Arms B are evaluable for efficacy after receiving at least 2 doses of doxorubicin.

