5.9 Duration of Follow-up

Patients in Arm A will be followed every 12 weeks after the 6-week (or 10-week if done) post-MLA scan until 1 year has elapsed since patient registration or until death, whichever occurs first. Following the first year, patients will continue to be followed every 6 months or at event occurrence for 5 years after patient registration or until death, whichever occurs first. Patients in Arm B will be followed every 8 weeks after the 6-week (or 10-week if done) post-MLA scan until 2 years have elapsed since patient registration or until progression, whichever occurs first. Following the first two years, patients will continue to be followed every 6 months or at event occurrence for 5 years after patient registration or until death, whichever occurs first. Follow-up consists of collection of Karnofsky performance status, DSC/DCE-MRI, and blood for biomarkers until disease progression (or 2 years of elapsed since patient registration or death, whichever occurs first). After documented disease progression, vital status and subsequent treatment will be obtained every 12 weeks for the remainder of the 2 years or until death, whichever occurs first. Patients removed from study for unacceptable adverse events that are possibly, probably, or definitely related to study procedures will be followed until resolution or stabilization of the adverse event. "Stabilization" is defined as remaining at a consistent CTCAE version 4.0 grade of the event for two consecutive assessments.

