9.0 CORRELATIVE STUDIES

9.1 DCE and DSC-MRI

All patients will undergo DSC and DCE-MRI at the following time points:

- no more than 3 weeks prior to MLA (OPTIONAL)
- within approximately 4 days after MLA
- 2-4 weeks (+/- 3 days) after MLA
- Every 12 weeks (+/- 7 days) following the last MRI for the first year or until disease progression for Arm A; every 8 weeks (+/- 7 days) until 2 years have elapsed or until disease progression, whichever comes first, for Arm B.

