9.2 Blood for Correlative Studies

Patients will have 7 mL blood for serum drawn at the following time points:

- before MLA; this sample can be collected any time during the 3 day before or the day of the procedure until the start of the procedure
- within approximately 3 days after MLA
- weeks 2-4 post-MLA (Arm A only, at time of DSC/DCE-MRI)
- weekly (+/- 3 days) prior to (on the same day as) doxorubicin (Arm B only)
- Every 12 weeks (+/- 7 days) for the first year or until disease progression for Arm A; every 8 weeks (+/- 7 days) until 2 years have elapsed or disease progression, whichever comes first, for Arm B. Blood draws will be drawn one same days as MRIs, prior to scan.

A minimum of 2 ml will be drawn and placed in a red top tube and a minimum of 5 ml will be collected into a green top (heparin) tube. Specimens should be immediately transported to the Tissue Procurement Core (TPC) for processing.

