12.3.6 Progression-Free Survival

PFS is defined as the duration of time from start of treatment to time of progression or death, whichever occurs first.

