PFS and OS will be estimated by Kaplan-Meier product limit method. The progression-free survival and overall survival probabilities at certain time points (e.g. 3 months, 6 months) will be presented as well. The difference in OS between Arm A and the historical control of bevacizumab alone will be compared by log-rank test. The quality of life (QOL) using Karnofsky or Lansky performance status will be characterized by summary statistics (mean, standard deviation and range).

The tumor-specific immune responses are collected at pre and post-MLA treatment. Paired t-test will be used to determine the effects of MLA treatment on patient's tumor-specific immune responses. Cox proportional hazard model will be used to determine the relationship between the duration of MLA-induced BBB disruption and PFS.

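### The Cox model of PFS on duration of blood-brain-barrier disruption uses an exposure that progression itself cuts short; entered as one fixed value, it can suggest a benefit that is not there

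*Combined protocol and SAP*

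**What the plan says.** The analysis has one sentence, in Section 14.0: a "Cox proportional hazard model will be used to determine the relationship between the duration of MLA-induced BBB disruption and PFS". Like the rest of that section, it applies within each arm of six.

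Section 12.3.6 sets the clock: "PFS is defined as the duration of time from start of treatment to time of progression or death, whichever occurs first". Section 1.6 says that the degree, extent and duration of leakage will come from serial DSC and DCE scans after the ablation. Those measurements end with the outcome. Section 5.9: "Follow-up consists of collection of Karnofsky performance status, DSC/DCE-MRI, and blood for biomarkers until disease progression". Section 9.1 schedules scans "every 8 weeks (+/- 7 days) until 2 years have elapsed or until disease progression, whichever comes first, for Arm B", after one at about 4 days and one at 2-4 weeks. Section 9.2 schedules blood "Every 12 weeks (+/- 7 days) for the first year or until disease progression for Arm A".

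On expected duration, Section 1.9 reports from adult imaging that "the BBB disruption lasts for several weeks following treatment before returning to a low baseline", and Section 1.5 works with a 6-week window.

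Nowhere do the documents define when disruption ends, say how to enter a duration still running at progression or death, or name a landmark or a time-dependent covariate. The pre-ablation scan, a natural reference, is optional.

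**The concern.** The exposure is not known at time zero. It builds up during PFS follow-up and stops being observed when the PFS event occurs. A patient can be recorded with long disruption only by staying progression-free long enough to be scanned again. Entered as a fixed baseline covariate, which is the natural reading of the sentence, this is immortal-time bias.

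The protocol's own figures make it relevant. With a 6-week window and Arm B scans every 8 weeks after the 2-4-week scan, the return to baseline is often first visible around weeks 10-12. Some relapsed patients may have progressed by then.

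The false signal would match what the rationale hopes to find, and Section 14.0 says that the data will be used to design future studies.

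**Working it through.** The plan gives no hazard ratio, event count or power for this model, so there is no figure to reproduce. The check asks what the model returns in Arm B when duration and PFS are unrelated (true HR 1.00).

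**Inputs from the documents.** Scans at days 1-4, at 2-4 weeks, then every 8 weeks ± 1 week; censoring at 104 weeks; scans before week 6 not read for response (Section 12.1).

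**Assumptions, not in the documents.** Disruption duration D is log-normal with log-SD 0.5 and median 6 weeks (2, 4 and 12 also tried). Exponential PFS has median 13 or 26 weeks; in the between-scan case this is the median time after week 6. There are 200,000 patients per scenario.

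**Two fixed codings.** (a) Time of the last scan still disrupted. (b) Time of the first scan back at baseline, otherwise the last available scan.

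Null HR per 4 weeks, D median 6 weeks, shown for median PFS 13 / 26 weeks:

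| Coding | Events found at scans, progression scan counted | Events found at scans, progression scan dropped | Events between scans, none before week 6 |
|---|---|---|---|
| True D (not observable) | 1.00 / 1.00 | 1.00 / 1.00 | 1.00 / 1.00 |
| (a) last disrupted scan | 0.98 / 0.99 | 0.82 / 0.89 | 0.90 / 0.95 |
| (b) first scan back, otherwise last | 0.90 / 0.93 | 0.47 / 0.58 | 0.60 / 0.72 |

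Repeat runs agree to within about 0.01.

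**Where the bias is small.** With D median 2 weeks, coding (a) gives 1.00-1.05, although (b) with between-scan events still gives 0.86 / 0.92. In Arm A, with an assumed median PFS of 2-5 years and no events before week 6, coding (a) gives 0.97-1.00.

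**Recurrence.** Section 1.6 attributes a late Ktrans rise in one of four adult examples to recurrence. If 25% of counted progression scans read as disrupted for that reason (an assumption), the HR per SD of duration under (a) moves from 0.89-1.01 to 0.80-0.88.

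**A second set of assumptions.** With log-SD 0.6, D medians of 3, 6 and 12 weeks, PFS medians of 13, 26 and 52 weeks, and 30% of events dated between scans, the last disrupted scan before progression gave HRs of 0.68-0.99 across 18 scenarios over both arms.

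**Six patients.** In a nominal 5% likelihood-ratio test with no events before week 6, false positives are 8-9% with fully observed D. They are 8-10% under (a) for D medians of 2-6 weeks, and 22-38% under (b) at 6 weeks.

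**Would the usual remedies work with six patients?** P(still disrupted at scan time s) = Φ(ln(6/s)/0.5). At s = 3 this is Φ(1.386) = 0.917; averaged over 2-4 weeks it is about 0.907.
- Yes/no landmark: all six alike in 0.907⁶ + 0.093⁶ ≈ 0.56 of arms. At most one differs in about 0.56 + 6 × 0.093 × 0.907⁵ ≈ 0.90.
- Time-dependent status indexed by scheduled visit: no finite HR in about 80-90% of arms.
- Landmark with a continuous early measure: null HR 0.985-1.00 per SD in large samples, and the exposure varies between patients.

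**The case against.** The strongest reply is that the large biases need unfavourable choices. Response is read at scheduled scans, with a tumor response form for each MRI (Section 11.0). If events are found at scans and the progression scan is counted, the 6-week HRs are 0.90-0.99. Coding (b) is not proposed anywhere. Early events are also limited: scans before week 6 are not read for response, and Section 5.5 says "All patients in Arms B are evaluable for efficacy after receiving at least 2 doses of doxorubicin". Weekly Arm B blood, and the 6- or 10-week scan that Section 5.9 mentions, could sharpen the duration and reduce truncation. The model serves no listed objective, and Section 1.6 leaves the link between disruption maps and outcome to a larger database.

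Much of this stands, and it limits the size and the stakes. It does not remove the problem. Nothing in the plan selects the favourable coding. Deterioration and death also count as events and can fall between scans. With between-scan events after the second doxorubicin dose, coding (a) still gives 0.79 / 0.88 at 6 weeks.

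Two stronger readings are tempting. A reader might set 0.98 against 0.60 and infer that coding alone moves the result that far. Those two cells also differ in how events are detected. For 13-week PFS, coding moves the HR from 0.90 to 0.60 with between-scan events, and from 0.98 to 0.90 with scan-found events and the progression scan counted. A reader might also infer that the model must lean towards benefit. Some codings sit at or slightly above 1, and recurrence-driven Ktrans makes the net direction uncertain.

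**Conclusion.** The concern holds in a limited form. A fixed-value Cox model on observed duration can suggest that longer disruption goes with longer PFS when it does not. At an assumed 6-week disruption and 13- or 26-week median PFS, the null HR per 4 weeks runs from near 1 (0.98 / 0.99) to 0.47 / 0.58, depending on the coding, the handling of the progression scan and how events are found. The distributions of D and PFS are assumptions; the scan schedule is the protocol's.

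The Kaplan-Meier estimates of PFS and OS are not affected, and no listed objective rests on this model. What is at risk is the pilot signal passed to later studies. This is a worthwhile, inexpensive improvement rather than a flaw in the trial's main results.

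**What to change.** Do not enter full observed duration as a fixed baseline covariate. Replace the sentence in Section 14.0 with wording such as:

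*Within each arm, the relation between early barrier disruption and PFS will be described by a landmark Cox model. The landmark is the 2-4-week scan. The exposure is continuous peritumoral Ktrans at that scan. PFS is counted from that scan, and only patients then progression-free are included. Ktrans values taken at or after progression are not used as exposure. The hazard ratio and its interval are descriptive.*

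The plan should also name the Ktrans summary (DCE or DSC, and the region) before the data are seen.

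The yes/no landmark and time-dependent status should not be the main analysis with six patients, for the reasons in the working. Time-dependent coding can be kept for a later, larger data set, indexed by scheduled visit. Carrying readings forward by actual scan date creates the opposite artefact when events are found at scans (null HR 2.7-5.6, against 0.96-1.01 by scheduled visit).

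Cost: wording only, with no new scans or blood. The analysis then addresses early degree of disruption, not full duration. Patients with events before the landmark drop out: about 2-5% of efficacy-evaluable Arm B patients at the assumed PFS, and none if no events occur before week 6. Estimates from six patients stay imprecise.

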APPENDIX 1: Karnofsky and Lansky Performance Status Scale

Karnofsky		Lansky	
Score	Description	Score	Description
100	Normal, no complaints, no evidence of disease	100	Fully active, normal.
90	Able to carry on normal activity, minor signs or symptoms of disease.	90	Minor restrictions in physically strenuous activity.
80	Normal activity with effort; some signs or symptoms of disease.	80	Active, but tires more quickly
70	Cares for self, unable to carry on normal activity or do active work.	70	Both greater restriction of and less time spent in play activity.
60	Required occasional assistance, but is able to care for most of his/her needs.	60	Up and around, but minimal active play; keeps busy with quieter activities.
50	Requires considerable assistance and frequent medical care.	50	Gets dressed, but lies around much of the day; no active play, able to participate in all quiet play and activities.
40	Disabled, requires special care and assistance.	40	Mostly in bed; participates in quiet activities.
30	Severely disabled, hospitalization indicated. Death not imminent.	30	In bed; needs assistance even for quiet play.
20	Very sick, hospitalization indicated. Death not imminent.	20	Often sleeping; play entirely limited to very passive activities.
10	Moribund, fatal processes progressing rapidly.	10	No play; does not get out of bed.

APPENDIX 2: PATIENT’S MEDICATION DIARY

Today’s Date: _____ Agent: Etoposide Cycle: _____

Patient Name: _____ Study ID#: _____

INSTRUCTIONS TO THE PATIENT:

1. Complete one form for each cycle. Take _____mg (____capsules) of etoposide as directed by your study doctor.
2. Record the date, the number of capsules taken, and when you took them.
3. If you forget to take it before bedtime, then do not take a dose that day. Restart taking it the next day.
4. If you have any questions or notice any side effects, please record them in the comments section. Record the time if you should vomit.
5. Please return the forms to your physician or your study coordinator when you go to your next appointment. Please bring your unused study medications and/or empty bottles with you to each clinic visit so that a pill count can be done.

Day	Date	What time was dose taken?	# of capsules taken	Comments
1				
2				
3				
4				
5				
6				
7				
8				
9				
10				
11				
12				
13				
14				
15				
16				
17				
18				
19				
20				
21				
22				
23				
24				
25				
26				
27				
28
